### 5.2.8. Standard Derivations and Reporting Conventions

The following conversion factors will be used to convert days into weeks, months or years:  
1 week = 7 days, 1 month = 30.4375 days, 1 year = 365.25 days.

Demographics and physical measurements:

- Age [years]:
  - $(\text{date of given informed consent} - \text{date of birth} + 1) / 365.25$
  - In case of missing day, day only: Age [years]:  $(\text{year/month of given informed consent} - \text{year/month of birth})$
  - In case only year of birth is given: Age [years]:  $(\text{year of given informed consent} - \text{year of birth})$

The integer part of the calculated age will be used for reporting purposes.

- $\text{BMI (kg/m}^2\text{)} = \text{weight (kg)} / [\text{height (m)}]^2$
- $\text{BSA (m}^2\text{)} = ([\text{height (cm)} \times \text{weight (kg)}] / 3600)^{0.5}$

For reporting conventions, mean and median should generally be displayed one more decimal place than the raw data and standard deviation should be displayed to two more decimal places than the raw data. Percentages will be reported to one decimal place. The rounding will be performed to closest integer / first decimal using the common mid-point between the two consecutive values. E.g., 5.1 to 5.4 will be rounded to an integer of 5, and 5.5 to 5.9 will be rounded to an integer of 6.

### **5.2.9. Unscheduled Visits**

Generally, data collected at unscheduled visits will be included and analyzed for both safety and efficacy analyses in the same fashion as the data collected at scheduled visits except where otherwise noted in the sections that follow. Descriptive statistics (mean, SD, median, minimum, maximum, quartiles) by nominal visit or time point for safety endpoints such as laboratory measurements, ECGs and vital signs will include only data from scheduled visits.

### **5.2.10. Adequate Baseline Tumor Assessment**

Adequate baseline is defined using the following criteria:

- All baseline assessments must be within 28 days prior to and including ‘start date’.
- All documented lesions must have non-missing assessments (ie, non-missing measurements for target lesions and non-missing lesions status at baseline for non-target lesions).
- Computerized tomography (CT) or magnetic resonance imaging (MRI) is required at baseline and may include chest, abdomen and pelvis CT or MRI scans, brain CT or MRI scan, and bone scans. The CT scans should be performed with contrast agents unless contraindicated for medical reasons.

### **5.2.11. Adequate Post-baseline Tumor Assessment**

An adequate post-baseline assessment is defined as an assessment where a response of CR, PR, SD, non-CR/non-PD, or PD can be determined (see [Section 6.2.2.1](#)). Time points where the response is NE or no assessment was performed will not be used for determining the censoring date.

## **5.3. Methods to Manage Missing Data**

### **5.3.1. Missing Data**

Unless otherwise specified, all data will be evaluated as observed, and no imputation method for missing values will be used.

In all patient data listings imputed values will be presented. In all listings imputed information will be flagged.

Missing statistics, eg, when they cannot be calculated, should be presented as 'ND' or 'NA'. For example, if N=1, the measure of variability (SD) cannot be computed and should be presented as 'ND' or 'NA'.

### **5.3.1.1. Pharmacokinetic Concentrations**

#### **Concentrations Below the Limit of Quantification**

For all calculations, figures and estimation of individual pharmacokinetic parameters, all concentrations assayed as below the level of quantification (BLQ) will be set to zero. In log-linear plots these values will not be represented. The BLQ values will be excluded from calculations of geometric means and their confidence intervals. A statement similar to 'All values reported as BLQ have been replaced with zero' should be included as a footnote to the appropriate tables and figures.

#### **Deviations, Missing Concentrations and Anomalous Values**

In summary tables and plots of median profiles, concentrations will be set to missing if one of the following cases is true:

1. A concentration has been reported as ND (ie, not done) or NS (ie, no sample);
2. A deviation in sampling time is of sufficient concern or a concentration has been flagged as anomalous by the clinical pharmacologist.

Summary statistics will not be presented at a particular time point if more than 50% of the data are missing. For analysis of pharmacokinetic concentrations, no values will be imputed for missing data.

### **5.3.1.2. Pharmacokinetic Parameters**

Whether actual or nominal PK sampling time will be used for the derivation of PK parameters will be determined by the results of interim PK analyses. If a PK parameter cannot be derived from a patient's concentration data, the parameter will be coded as NC (ie, not calculated). NC values will not be generated beyond the day that a patient discontinues.

In summary tables, statistics will be calculated by setting NC values to missing. Statistics will not be presented for a particular treatment if more than 50% of the data are NC. For statistical analyses (ie, analysis of variance), PK parameters coded as NC will also be set to missing.

If an individual patient has a known biased estimate of a PK parameter (due for example to a deviation from the assigned dose level), this will be footnoted in summary tables and will not be included in the calculation of summary statistics or statistical analyses.

### **5.3.2. Handling of Incomplete Dates**

#### **5.3.2.1. Disease History**

Incomplete dates for disease history (eg, initial diagnosis date, date of documented, locally advanced, inoperable or metastatic disease diagnosis, date of response or progression in prior treatment) will be imputed as follows:

- If the day is missing, it will be imputed to the 1st day of the month.
- If both day and month are missing, the month and day will be imputed as January 1st.
- If the date is completely missing, no imputation will be performed.

#### **5.3.2.2. Adverse Events**

Incomplete AE-related dates will be imputed as follows:

- If only the day part of the AE onset date is missing, then the AE onset date will be replaced by 1st of the month. For example, if the AE onset date is --/JAN/2015, then the imputed AE onset date will be 01/JAN/2015.
- If both the day and month of the AE onset date are missing, then the onset date will be replaced by January 1st of the year. For example, if AE onset date is --/---/2014, then the imputed AE onset date will be 01/JAN/2014. In all other cases the missing onset day or missing onset month will be replaced by 1.
- If after above imputation, the imputed onset date with same month and year of the start of study treatment but less than the start of study treatment, and stop date is not less than the start of study treatment, then the imputed AE onset date will be re-assigned as the start of study treatment.
  - If the AE onset date is missing completely, then the onset date will be imputed as following: If not missing the visit date and visit date is less than the start of study treatment and less than or equal to the stop date, then the visit date will be used to impute the onset date.
  - Else if previous visit date is greater than or equal to the start of study treatment and less than or equal to the stop date, then the previous visit date will be used to impute the onset date.
  - Else if previous visit date is less than the start of study treatment and the start of study treatment is less than or equal to stop date, then the start of study treatment will be used to impute the onset date.
  - Else Stop date will be used to impute the onset date.
- Incomplete stop date will be replaced by the last day of the month (if day is missing only).

- Incomplete stop date will be replaced by the last month of the year (if month is missing).
- If the AE stop date is missing completely and still present, then the stop date will be imputed as following:
  - If not missing death date, then death date will be used to impute the stop date.
  - Else if not missing withdrawal date or Date Decision to Discontinue Treatment, the stop date will be imputed as the maximum of Withdrawal date, Date Decision to Discontinue Treatment, Onset date or AE visit date.
  - Else if missing withdrawal date and Date Decision to Discontinue Treatment, the stop date will be imputed as the maximum of subject summary visit date, Onset date or AE visit date.
  - Else the stop date will be imputed as the maximum of onset date or last dosing date.
- If the AE stop date is missing completely and event resolved, then the stop date will be imputed as following:
  - If visit date is greater than onset date, then the visit date will be used to impute the stop date.
  - Else the onset date will be used to impute the stop date.
- If after above imputation, the imputed stop date is less than the start of study treatment, then the imputed AE stop date will be re-assigned as the start of study treatment.
- In all other cases the incomplete stop date will not be imputed. If stop date of AE is after date of cut-off outcome of AE is ongoing at cut-off.

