20. **Adverse Event (AE) Assessments:** Adverse events should be documented and recorded at each visit using NCI CTCAE version 4.03. Patients must be followed for AEs for 28 days after the last treatment administration or until all drug related toxicities have resolved, whichever is later; or earlier than 28 days should the patient commence another anticancer therapy in the meantime. For serious adverse events (SAEs), the active reporting period to Pfizer or its designated representative begins from the time that the patient provides informed consent, which is obtained prior to the patient's participation in the study, ie, prior to undergoing any study-related procedure and/or receiving investigational product, through and including 90 calendar days after the last administration of the investigational products and before initiation of a new anti-cancer treatment. The prolonged follow up is due to the pharmacokinetic properties of the investigational product MK-3475. SAEs experienced by a patient after the active reporting period (see [Section 8.2](#)) has ended should be reported to the Sponsor if the Investigator becomes aware of them; at a minimum, all SAEs that the Investigator believes have at least a reasonable possibility of being related to study drug are to be reported to the Sponsor. AEs (serious and non-serious) should be recorded on the Case Report Form (CRF) from the time the patient has taken at least one dose of study treatment through last patient visit (Day 28 after last dose). If a patient begins a new anticancer therapy, the AE reporting period for non-serious AEs ends at the time the new treatment is started. Pregnancy or breast feeding that occur during the trial, within 120 days of discontinuing treatment with MK-3475, or within 28 days after the cessation of study treatment if the patient begins a new anticancer therapy, whichever is earlier, should be reported as in [Section 8.10](#) (Exposure During Pregnancy).
21. **Concomitant Medications:** All concomitant medications including supportive care drugs (eg, anti-emetic treatment and prophylaxis), and the drugs used to treat AEs or chronic diseases should be recorded in the CRF.

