## **3.5. Safety Endpoints**

### **3.5.1. Adverse Events**

#### **Treatment-Emergent Adverse Events**

Treatment-emergent adverse events (TEAEs) are those events with onset dates occurring during the on-treatment period for the first time, or if the worsening of an event is during the on-treatment period.

**On-treatment period** is defined as the time from the first dose of study treatment through minimum (30 days + last dose of study treatment, start day of new anti-cancer drug therapy – 1 day). The start day of new anti-cancer drug therapy after the first dose of study treatment is derived as outlined in [Section 5.2.5](#).

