### 6.6.1. Adverse Events

Treatment-emergent adverse events (TEAEs) are those events with onset dates occurring during the on-treatment period for the first time, or if the worsening of an event is during the on-treatment period as defined in [Section 3.5.1](#).

All analyses described will be based on TEAEs (started during the on-treatment period) if not otherwise specified. The AE listings will include all AEs (whether treatment-emergent or not). AEs outside the on-treatment period will be flagged in the listings.

- **Related Adverse Events:** adverse events with relationship to study treatment (as recorded on the AE eCRF page, Relationship with study treatment = Related) reported by the investigator and those of unknown relationship (ie, no answer to the question 'Relationship with study treatment').
- **Serious Adverse Events (SAE):** serious adverse events (as recorded on the AE eCRF page, Serious Adverse Event = Yes).
- **Adverse Events Leading to Permanent Treatment Discontinuation:** adverse events leading to permanent discontinuation of study treatment (as recorded on the AE eCRF page, Action taken with study treatment = Drug withdrawn).
- **Adverse Events Leading to Death:** adverse event leading to death (as recorded on the AE eCRF page, Outcome = Fatal, as well as AEs of Grade 5).
- **Immune-related Adverse Events (irAE):** irAEs (as identified according to a pre-specified search list of MedDRA PTs, documented in the Merck ECI document and finalized for analysis of the current studies data prior to DB lock).
- **Infusion-related Reactions (IRR):** IRRs (as identified according to a pre-specified search list of MedDRA PTs, documented in the Merck ECI document and finalized for analysis of the current studies data prior to DB lock) with onset on study drug dosing date (not prior to infusion of study drug) or the day following study drug infusion.

Unless otherwise specified, AEs will be summarized by number and percentage of patients with the AE in the category of interest as described above, by treatment group, primary SOC and PT in decreasing frequency observed in all treatment groups combined.

Each patient will be counted only once within each SOC or PT. If a patient experiences more than one AE within a SOC or PT for the same summary period, only the AE with the strongest relationship or the worst severity, as appropriate, will be included in the summaries of relationship and severity.

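### An AE onset known only to the first-dose year is imputed before treatment when first dose fell in February to December, and so drops out of the treatment-emergent summaries unless on-treatment worsening is recorded

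*SAP*

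**What the plan says.** SAP 5.3.2.2 handles incomplete AE onset dates in stages.

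- Day missing: the first of the month is used.
- Day and month missing: 1 January is used. The SAP illustrates this with "if AE onset date is --/---/2014, then the imputed AE onset date will be 01/JAN/2014".
- Correction: an imputed date is moved to first dose for "the imputed onset date with same month and year of the start of study treatment but less than the start of study treatment". A further condition is that the event must have stopped on or after first dose.
- Onset wholly missing: a separate sequence uses visit dates, first dose or the stop date.
- Later in the section, an imputed stop date that falls before first dose is reset to first dose. This changes the stop date, not the onset.

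SAP 3.5.1 defines treatment-emergent AEs (TEAEs) as "those events with onset dates occurring during the on-treatment period for the first time". An event that worsens within that period also counts. The on-treatment period is "the time from the first dose of study treatment through minimum (30 days + last dose of study treatment", or to the day before a new anti-cancer drug therapy if that is earlier. SAP 6.6.1 adds: "All analyses described will be based on TEAEs (started during the on-treatment period) if not otherwise specified". Under SAP 5.2.7 and 6.6.1, events outside the period are kept in the listings with a flag and are not summarized.

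On collection, Protocol Schedule of Activities footnote 20 says "AEs (serious and non-serious) should be recorded on the Case Report Form (CRF) from the time the patient has taken at least one dose". Footnote 7 and Protocol 7.1.2 also place baseline signs and symptoms on the AE page.

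**The concern.** A year-only date always becomes a January date, so the month test can succeed only for a patient first dosed in January. For all others the correction cannot act on a year-only onset in the start year.

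The result sits badly with the rest of the section. An event with the day missing in the start month is moved to first dose. An event with no onset date at all is also placed at first dose if the previous visit was before first dose and the stop date was not. Knowing the year can therefore give a worse classification than knowing nothing.

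The overall safety profile is a secondary objective, and the AE tables are presented by dose group with few patients in each. A rule that places true on-treatment events before treatment can only lower the counts in those tables.

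**Working it through.** The documents give no figure on this point, so there is nothing to reproduce. The rule was applied as written.

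**Notation.** F = first dose, S = stop date, o = imputed onset. The onset is reset to F only if month(o) = month(F), year(o) = year(F), o < F and S ≥ F. S ≥ F is assumed throughout.

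**Worked records.**

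| First dose | Recorded onset | Imputed | Month and year match? | Final onset |
|---|---|---|---|---|
| 15 Mar 2015 | year 2015 only | 1 Jan 2015 | no | 1 Jan 2015 |
| 15 Mar 2015 | Mar 2015, day missing | 1 Mar 2015 | yes | 15 Mar 2015 |
| 15 Jun 2015 | year 2016 only | 1 Jan 2016 | not needed, already after F | 1 Jan 2016 |
| 20 Jan 2015 | year 2015 only | 1 Jan 2015 | yes | 20 Jan 2015 |

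In the first row the onset lies 31 + 28 + 14 = 73 days before first dose, even with a stop date of, say, 20 June 2015.

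**All first-dose dates in a 365-day year.**

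| Recorded onset | Start dates giving a pre-treatment onset |
|---|---|
| Year only, equal to the first-dose year | 365 − 31 = 334 of 365 (334/365 = 91.5%) |
| Year only, next calendar year | 0 of 365 |
| Day missing, start month known | 0 of 365 |

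The 334 are exactly the starts from 1 February to 31 December. If the known part of the date is matched instead, the first row becomes 0 of 365.

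The same fault arises when the month is missing but the day is known, because the SAP sets the missing month to 1.

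**Share of true on-treatment, year-only AEs affected.** This needs assumptions that the documents do not supply: first-dose dates uniform over the year, and true onset uniform from first dose to 30 days after last dose.

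| Last dose at day | Corresponds to | Share imputed before treatment |
|---|---|---|
| 0 | one dose | 0.874 |
| 21 | two cycles | 0.845 |
| 183 | 6 months | 0.623 |
| 365 | 12 months | 0.387 |
| 31 × 21 = 651 | 32 cycles | 0.225 |

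The share falls with longer treatment because more onsets fall in a later calendar year, where the rule works.

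**The case against.** **Frequency.** Visits are weekly in Cycles 1 and 2, AEs are recorded at every visit, and SAEs and events of clinical interest go to the sponsor within 24 hours. A new serious event known only to the year is improbable. This stands: the practical size is likely to be small.

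**Some records are rightly pre-treatment.** Baseline signs and symptoms sit on the same CRF page, and older complaints are plausible candidates for a year-only onset. This also stands. A reader might infer from the SAP's 2014 example, together with the original protocol date of 17 April 2014, that every year-only 2014 AE is lost. All such onsets are indeed imputed before treatment, but for baseline entries that is correct. The example also shows a date format rather than a trial record; SAP 5.3.2.3 uses the same illustration for medications.

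**Not every treatment-emergent table is closed to the event.** Recorded worsening during treatment is a second route under SAP 3.5.1, although the parenthesis in SAP 6.6.1 about events having started on treatment leaves that route unclear. The Deaths tables in SAP 6.6.2 come from the death and survival follow-up forms and do not depend on TEAE status.

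**Dose selection.** A reader might infer that the MTD is affected. The documents do not support this. Under Protocol 3.2, DLT data go to the study statistician for the model update, and SAP 6.1.1.1 summarizes DLTs on the DLT-evaluable set, outside the TEAE tables.

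None of this supplies the missing year-only branch.

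**Conclusion.** The rule is wrong as written, within a narrow scope: onset known only to the year, that year equal to the first-dose year, and first dose in February to December. A truly on-treatment AE of this kind is left out of the TEAE-based summaries in SAP 6.6.1, 6.6.3 and 6.6.4 unless on-treatment worsening is recorded. For such events the misclassification runs one way, towards lower apparent toxicity in the dose group.

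The 334 of 365 follows from the rule alone. The shares from 0.225 to 0.874 rest on the uniform assumptions and apply only to year-only records, whose number is not given.

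It would be tempting to say that one lost patient moves a dose group's rate by 11 to 33 percentage points (1/9 to 1/3, taking 3 to 9 patients per level). That holds only for a table row in which the patient has no other event, since each patient counts once per term, and only where no expansion patients enlarge the group. It is a worst case, not an expected effect.

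**What to change.** In SAP 5.3.2.2, replace the condition on the imputed onset date with:

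> If the imputed onset date is before the start of study treatment, the known part of the onset date (year, or month and year) equals that of the start of study treatment, and the stop date (before any reset of the stop date to the start of study treatment) is missing/ongoing or not before the start of study treatment, the onset date is set to the start of study treatment. This does not apply to records entered as baseline signs and symptoms.

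Two parts of this wording matter. The stop date must be taken before the later reset; otherwise, depending on programming order, an event that ended before treatment could pass the test and become treatment-emergent. The exclusion keeps baseline complaints where they belong.

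The cost is one sentence in the SAP and about one line of code, plus a way to identify baseline entries. The downside is small: a few pre-existing complaints not identified as baseline may be counted as treatment-emergent, as already happens for dates with only the day missing.

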#### **5.3.2.3. Prior and Concomitant Medications**

Incomplete prior/concomitant medication dates will be imputed as follows:

- If the medication date is missing completely, no imputation will be performed.
- If the day of medication date is missing, then the medication date will be replaced by 1st of the month. For example, if the medication start date is --/JAN/2015, then the imputed medication start date will be 01/JAN/2015.
- If both the day and month of medication start date are missing, then the medication date will be replaced by January 1st of the year. For example, if the medication start date is --/--/2014, then the imputed medication start date will be 01/JAN/2014.
- In all other cases the missing medication day or missing medication month will be replaced by 1.

- Incomplete stop date will be replaced by the last day of the month (if day is missing).
- Incomplete stop date will be replaced by the last month of the year (if month is missing).
- In all other cases the incomplete medication stop date will not be imputed.

